1.1 Background

Psoriatic arthritis (PsA) is an immune-mediated chronic inflammatory disease belonging to the spectrum of conditions commonly referred to as spondyloarthritis (SpA). While the various SpA may be diverse in their clinical presentations, common environmental as well as genetic factors associated with susceptibility to SpA are suspected ([Turkiewicz and Moreland 2007](#)). This latter notion was corroborated by findings in a large-scale single nucleotide polymorphism scan study, where interleukin (IL)-23R variants that were previously linked to Crohn's disease and psoriasis (diseases that may both co-exist with SpA) conferred risk to developing ankylosing spondylitis (AS) ([Barrett et al 2008](#)). Together, a common pathway, including the IL-23/IL-17 axis, may play a role in seronegative SpAs, including PsA.

PsA is a frequent and chronic immune-mediated disease encompassing a spectrum of overlapping clinical entities ([Moll and Wright 1973](#)). Up to 40% of patients with psoriasis will develop PsA, which is both more common and more severe than previously believed ([Taylor et al 2006](#)). PsA is also associated with significant morbidity and disability, and constitutes a major socioeconomic burden.

Nonsteroidal anti-inflammatory drugs (NSAIDs) may improve symptoms in patients with mild PsA, but can worsen skin disease and be associated with an increased risk of cardiovascular side effects. Similarly, intra-articular injections of corticosteroids and low doses of systemic corticosteroids have been used with variable efficacy and significant side effects with chronic use. Disease-modifying anti-rheumatic drugs (DMARDs) are more typically used for PsA, and include methotrexate (MTX), sulfasalazine, cyclosporine, and leflunomide; however, these therapies may only partially control established disease ([Mease 2008](#); [Mease and Armstrong 2014](#)). Biologic agents such as the tumor necrosis factor (TNF) inhibitors adalimumab, certolizumab pegol, etanercept, golimumab, and infliximab are approved in patients with PsA to reduce joint disease activity, prevent structural damage, and improve function ([Mease et al 2000](#), [Mease et al 2005](#)). However, TNF-inhibitor therapy may result in significant dose-limiting adverse effects, including the development of autoantibodies and the induction of a lupus-like syndrome.

Additional approved therapies for patients with PsA [REDACTED]

[REDACTED] Several lines of evidence support additional therapeutic pathways in PsA. Prominent T cell involvement occurs in the pathogenesis of PsA ([Tassiulas et al 1999](#); [Curran et al 2004](#); [Mease and Armstrong 2014](#)) and clinical trials have shown efficacy of T cell-targeted treatment that has included cyclosporine A, CTLA4-Ig, and alefacept. Despite available therapies for PsA, an unmet clinical need remains for agents that can be used singly or in combination with other therapies and provide effective short and long-term disease control especially on those PsA specific clinical findings such as dactylitis and enthesitis with favorable risk/benefit profiles.

IL-17 antagonism represents a novel therapeutic approach aimed at interference with the chronic inflammatory process by selectively targeting the predominant pro-inflammatory cytokine of the helper T17 cell subset. Additional effects of anti-IL-17 on bone homeostasis

via receptor activator of nuclear factor kappa-B ligand (RANKL) and IL-1, upstream of TNF α , can be inferred from animal studies (Koenders et al 2005). Assuming a potential role of IL-17 cells in the inflammatory infiltrate in PsA, it can be speculated that locally disturbed homeostasis of osteoclastogenic and osteoblastogenic mechanisms characteristic of PsA might be affected by IL-17 blockade, thus potentially providing a therapeutic advancement to effectively treat dactylitis and enthesitis in PsA.

Secukinumab (AIN457) is a high-affinity fully human monoclonal anti-human antibody that neutralizes IL-17A activity. IL-17A is the key cytokine in the newly discovered Th17 pathway that is believed to be an important mediator of autoimmunity. Neutralization of IL-17A has strong preclinical and clinical target validation.

A proof-of-concept study conducted in patients with PsA (CAIN457A2206) suggesting a clinically meaningful response for signs and symptoms up to Week 16. The efficacy of secukinumab in PsA patients is further supported by positive results for signs and symptoms (i.e. ACR20/50, PASI75/90), resolution of dactylitis, enthesitis and inhibition of radiologic damage at Week 24 obtained in a phase III study (CAIN457F2306; N=606) employing an intravenous (i.v.) loading regimen (3x10 mg/kg) of secukinumab Q2W followed by secukinumab s.c. 75 mg or 150 mg administered Q4W. In another phase III study (CAIN457F2312; N=397) secukinumab also demonstrated positive efficacy results superior to placebo in patients with PsA through most components of the arthritic and skin measures of signs and symptoms and physical function in a population comprised of 65% naïve to TNF- α inhibitors and 35% patients who were inadequate responders to a TNF- α inhibitor. Based on the results of these phase 3 trials, secukinumab received FDA approval in January 2016 for the treatment of active PsA and AS in adult patients. Therefore, treatment with secukinumab may result in improvement of symptoms and functional joint manifestations in afflicted patients.

The completed studies of secukinumab recruited both biologic exposed or naïve PsA patients with or without psoriatic skin lesions at baseline. Therefore a need for predefined prospective data exist for these different subgroups of patients which the precise effects of targeting IL-17A can be observed more clearly. The present study will evaluate the safety and efficacy of treatment with two doses of secukinumab compared with placebo in patients with active psoriatic arthritis and concomitant psoriasis who are naïve to biologic medications including tumor necrosis factor alpha (TNF α), IL-6 and IL-12/23 inhibitors. Also in the blinded long term extension period of this study, the effect of increasing the dose in non-responders after each evaluation every 12 weeks visit will provide valuable information regarding the correlation between the level of disease activity and IL-17A inhibition.

1.2 Purpose

The purpose of this study is to provide 16 week safety, efficacy and tolerability data in biologic naïve PsA patients with concomitant psoriatic skin lesions and evaluate the effect of secukinumab on PsA specific clinical findings such as dactylitis, enthesitis and psoriatic lesions. The study will also evaluate the early efficacy of the treatment at the first scheduled clinical visit after starting a treatment (i.e., at week 4) and investigate the remission status of all patients at each time points by evaluating the MDA, PASDAS and DAS28-CRP. This will be done in the blinded long term extension by increasing the dose to 300 mg in nonresponding

patients in 150 mg groups to confirm or support the role of higher IL-17A activity in PsA by evaluating the clinical response at every 12 weeks.

2 Study objectives

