	
4), followed by dosing every four weeks.
 
• Group 3- Placebo: placebo (two s.c. injection of 150 mg secukinumab placebo per dose) once per week for five weeks (at Baseline, Weeks 1, 2, 3, and 4), followed by dosing every four weeks. 
At each study treatment visit two s.c. injections in the form of PFS will be administered. This is necessary to maintain the blind, as secukinumab in PFS is available in either 1.0 mL (150 mg) or 2 x 1.0 mL (300mg). Placebo to secukinumab is also available in 1.0 mL to match the active drug.
 
Rescue medication is not allowed until Week 16.
 
Treatment Period 2
 
• Patients receiving secukinumab 300 mg (Group 1) will continue to receive the same dose up to Week 48.• At Weeks 16, 28 and 40 patients on secukinumab 150 mg (Group 2) will be classified as responders ($\geq 20\%$ improvement from BL in both tender and swollen joint counts) or non-responders.
• At Weeks 16, 28 and 40 patients on secukinumab 150 mg (Group 2) who are responders will continue to receive secukinumab 150 mg (1.0 mL) plus placebo (1.0 mL) every 4 weeks until next evaluation of responder status at weeks 28 or 40.• Patients who did not meet the responder criteria at Week 16, 28 or 40 will start receiving secukinumab 300 mg s.c. every 4 weeks and will continue this dose up to Week 48.• Patients on placebo (Group 3) regardless of their responder status will start receiving secukinumab 300 mg s.c. every 4 weeks from Week 16 up to Week 48.
Population	
The study population will be comprised of approximately 250 patients who have passed screening assessments, comply with eligibility criteria and have provided written consent.
 
• Male and female patients aged at minimum 18 at time of consent, with active PsA fulfilling the CASPAR criteria.• Patients must have symptoms for at least 6 months with moderate to severe PsA and must have ≥ 3 tender joints out of 78 and ≥ 3 swollen joints out of 76 at BL (dactylitis of a digit counts as one joint each).• Patients must have a target skin lesion and a PASI score of 1 or greater.• Patients must report active disease despite current or previous NSAIDs and / or DMARDs. Concomitant therapy with MTX (≤ 25 mg/week) will be acceptable, if dose and route of administration have been stable for at least four weeks prior to the

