9.7 Sample size calculation

The sample size was calculated based on the primary efficacy variable (i.e., ACR20 response) for the primary comparison (i.e., secukinumab 300 mg versus placebo). ACR20 response rates of 50% for secukinumab 300 mg and 20% for placebo (corresponding to an odds ratio of 4) at Week 16 were assumed, based on results from AIN457F2312 (FUTURE 2) study. Using a continuity-corrected chi-squared test, an allocation ratio of 2:1, a two-sided significance level of 0.05, and a power of 0.90, approximately 88 patients in secukinumab 300 mg group and 44 patients in placebo group will be needed (nQuery Advisor 7.0). Assuming a loss to follow-up rate of 10% and a 2:2:1 allocation ratio (secukinumab 300 mg: secukinumab 150 mg: placebo), the total number of randomized patients will be approximately 250 (100 on secukinumab 300 mg, 100 on secukinumab 150 mg, and 50 on placebo)

10 Ethical considerations

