2.2 Analysis sets

The following analysis sets will be used for the statistical reporting and analyses:

Randomized Set: The Randomized Set includes all randomized patients.

Safety Set: The Safety Set includes all patients who received at least one dose of study medication. Patients will be included in the analysis according to treatment received.

Full Analysis Set (FAS): The Full Analysis Set comprises all patients to whom study medication has been assigned. Patients inappropriately randomized (e.g., IRT was called in error for randomization of a screen failed patient) will be excluded from this analysis set.

Psoriasis Subset: The Psoriasis Subset comprises patients in whom at least 3% of body surface area was affected by psoriatic skin involvement at baseline.

Dactylitis Subset: The Dactylitis Subset comprises patients who have LDI >= 1 at baseline.

Up-titrated Subset: Up-titration Subset includes all completed patients who were up-titrated from 150 mg to 300 mg in Treatment Period 2, based on the response.

For efficacy analyses, following the intent-to-treat principle, patients will be analyzed according to the treatment they were assigned to at randomization.

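### 150 mg non-responders raised to 300 mg have no like-for-like reference in the visible plan, so their later improvement cannot support the stated purpose of the dose increase

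*Protocol*

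**What the plan says.** Protocol 1.2 presents the blinded extension, with its increase to 300 mg in 150 mg non-responders, as a way "to confirm or support the role of higher IL-17A activity in PsA by evaluating the clinical response at every 12 weeks". Protocol 1.1 adds that "the effect of increasing the dose in non-responders after each evaluation every 12 weeks visit will provide valuable information".

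Under Protocol 3.1 and 5.2, a Group 2 (150 mg) patient is a responder if tender and swollen joint counts have both improved by at least 20% from baseline. Status is assessed at Weeks 16, 28 and 40. All Group 2 non-responders move to 300 mg, and responders stay on 150 mg until the next assessment. For the other active arm, "Patients receiving secukinumab 300 mg (Group 1) will continue to receive the same dose up to Week 48", whatever the response.

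SAP 2.1 presents Treatment Period 2 by patients who switched and patients who continued on 150 mg. It treats efficacy after Week 16 as descriptive unless otherwise specified. SAP 2.4.1 lists the whole-period efficacy groups: 300 mg, 150–150 mg (R), 150–300 mg (NR), any 150 mg, and placebo–300 mg. SAP 2.2 defines a further set: "Up-titration Subset includes all completed patients who were up-titrated from 150 mg to 300 mg in Treatment Period 2". SAP 2.2.1 makes the Section 2.2 subsets planned subgroups of interest.

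**The concern.** The two introductory statements are about the effect of a dose increase. To learn that effect, one needs to know what the same patients would have done without the increase, and no 150 mg non-responder is left on 150 mg to show it.

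The groups displayed beside the switchers do not fill the gap. The 150–150 mg patients are there because they responded, so they are selected in the opposite direction. The 300 mg arm mixes responders and non-responders. The Up-titrated Subset adds a favourable selection of its own by keeping completers only.

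Switchers are picked because they failed at one visit. For a patient with a count of 3, 4 or 5 at baseline (3 is the entry minimum for each count), one joint is 33%, 25% or 20% of that count, so a single joint can decide whether it passes. Some of these patients will pass 12 weeks later on unchanged exposure. If that gain is read as a dose effect, the extension will seem to support a conclusion that it cannot support.

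**Working it through.** **1. The plan's own figure.** The documents give no figure for the up-titration question. The arm sizes come from Protocol 9.7: "ACR20 response rates of 50% for secukinumab 300 mg and 20% for placebo"; "Using a continuity-corrected chi-squared test, an allocation ratio of 2:1, a two-sided significance level of 0.05, and a power of 0.90". Without continuity correction, the placebo n is [1.96·√(1.5·0.4·0.6) + 1.2816·√(0.2·0.8 + 0.5·0.5/2)]² / 0.3² = (1.176 + 0.684)²/0.09 = 38.4, so 39. With correction it is (38.4/4)·[1 + √(1 + 6/(38.4·2·0.3))]² = 43.3, so 44, with 88 on 300 mg. Both agree with the Protocol. Allowing 10% loss, 44/0.9 gives 49 and 88/0.9 gives 98. The total is 49 + 98 + 98 = 245, in line with about 250. With 100 randomised to each active arm and 10% loss, about 90 per arm remain.

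**2. Response 12 weeks later with no dose effect.** Let p be the probability of meeting the joint-count rule, equal at both visits (no dose effect, no time trend), and r the correlation between visits 12 weeks apart.
- r is not in the documents. It is varied from 0.4 to 0.9.
- p is not in the documents either. Protocol 3.3 gives Week 24 ACR20 rates of 50.0% and 51.0% at 150 mg in two earlier studies. ACR20 requires the joint rule plus three of five other domains, so these rates are a floor for the joint rule in those populations. p is varied from 0.5 to 0.7.

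Model A uses one bivariate-normal latent response. The quantity is P(response at Week 28 | non-response at Week 16) = (p − p₁₁)/(1 − p), where p₁₁ is the probability of response at both visits. At p = 0.5 this equals arccos(r)/π: 33.3% at r = 0.5 and 20.5% at r = 0.8. Model B simulates tender and swollen counts separately (cross-correlation 0.5 or 0.7) and requires both to pass. The table gives the lowest and highest result over the two models, in percent.

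| p | r = 0.4 | r = 0.5 | r = 0.6 | r = 0.7 | r = 0.8 | r = 0.9 |
|---|---|---|---|---|---|---|
| 0.5 | 36.9–37.8 | 33.3–34.2 | 29.5–30.8 | 25.3–26.5 | 20.5–21.6 | 14.4–15.4 |
| 0.6 | 44.5–45.6 | 40.2–41.7 | 35.6–37.0 | 30.6–32.2 | 24.8–26.0 | 17.4–18.4 |
| 0.7 | 52.7–54.2 | 47.7–49.2 | 42.4–44.2 | 36.5–38.2 | 29.6–31.4 | 20.8–22.3 |

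For p = 0.5–0.6 and r = 0.5–0.8 the result is about 20–40%. Over the whole grid it is about 14–54%.

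**3. A reference inside the trial, and its precision.** Group 1 patients who fail the same rule at Week 16 keep their dose under the same blind. Joint counts are taken in every arm, and the responder-status row of Table 6-1 is not limited to Group 2. The number per group is 90·(1 − p): 45, 36 and 27 at p = 0.5, 0.6 and 0.7. The 95% CI half-width for a difference, at a common rate b, is 1.96·√(2b(1 − b)/n). It runs from 0.165 (n = 45, b = 0.2) to 0.261 (n = 27, b = 0.4), or about 17–26 points.

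**4. Weeks 28 and 40 need matching on history.** Patients up-titrated at Week 28 were responders at Week 16. With equal correlation between visits and no dose effect, their response at Week 40 is 50% at p = 0.5, and 55.3% (r = 0.5) to 52.6% (r = 0.8) at p = 0.6. Group 1 patients failing at Week 28 whatever their history would respond at the step 2 rates (model A). At r = 0.5 and 0.8 these are 33.3% and 20.5% for p = 0.5, and 40.2% and 24.8% for p = 0.6. The unmatched comparison would thus show a spurious gain of about 15–30 points (55.3 − 40.2 = 15.1; 50.0 − 20.5 = 29.5). First failures at Week 28 number about 90·(1 − p)·P(response | earlier non-response), by symmetry: from 90·0.4·0.248 ≈ 9 to 90·0.5·0.333 ≈ 15.

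**The case against.** The best reply is that the plan does not claim what is being attacked. No before-after test, estimand or decision rule for up-titration is written. Visible Week 52 outputs are counts, percentages and changes from baseline by sequence. Up-titration appears in none of the objectives in Protocol 2.1–2.2 or SAP 1.2. The rest of the Purpose paragraph (16-week safety and efficacy, Week 4 efficacy, remission status) does not depend on it. All of this stands. A reader might infer that the SAP judges the dose effect by a before-after change, or that the whole stated purpose fails. The text supports neither.

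Nor can one say that Group 1 non-responders are definitely left unused. SAP 2.13 is named in the update log but absent from the public text, and the Up-titrated Subset has no visible analysis section. An up-titration analysis could sit there.

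A reader might also take 20–40% as a property of this trial. It is not: it rests on an assumed correlation and response rate, concerns the Week 16 switch only, and contains no time trend, so it does not measure late response.

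What the reply does not remove is the causal wording of 1.1 and 1.2, together with a named subset planned for reporting and no visible reference group that could support that wording.

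**Conclusion.** The point holds as a limit on interpretation. Since every 150 mg non-responder is switched, and the visible comparison groups are selected differently, improvement after the switch cannot be attributed to the dose. The share that would appear with no dose effect could be substantial: about 20–40% under response rates of 50–60% and correlations of 0.5–0.8, and 14–54% over the wider grid, all on assumed inputs. Even the low end is large enough to mislead a reader who sees only the up-titrated group. The Week 16 primary test and the formal objectives are not touched. The improvement is worth making and cheap, but it is not a flaw in the main result.

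**What to change.** - In the Week 52 analysis, show Group 1 patients who fail the joint-count rule at Week 16 beside the 150 mg patients up-titrated at Week 16. Report response at Week 28, change from the switch visit, and the difference with a 95% CI, labelled descriptive.
- Include all up-titrated patients, with non-responder imputation, and not completers only.
- If Weeks 28 and 40 are shown, restrict the Group 1 reference to patients failing for the first time at that visit, and state the small numbers (about 9–15 per arm at Week 28 under the illustration).
- In Protocol 1.2, replace the wording about confirming or supporting with 'describe', and state that a before-after change in the up-titrated group alone will not be read as a dose effect.
- Reconcile the switch visits, because they define the comparison. Protocol 3.3 lists every clinical visit from Week 20 to Week 48 as well as Week 16, while 3.1, 5.2 and the Table 6-1 footnote give Weeks 16, 28 and 40.

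The cost is a few tables from data already collected and a weaker claim. No dosing rule changes. The groups are formed after randomisation. If the doses do not differ, Week 16 non-responders in the two arms are comparable by randomisation and the reference is valid. If 300 mg is better, its non-responders are the more resistant patients, and the difference is biased as an estimate of the dose effect. Either way it is imprecise, with a CI half-width of about 17–26 points.

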2.1 Primary objective(s)

To demonstrate that the efficacy of secukinumab 300 mg at Week 16 is superior to placebo in patients with active PsA based on the proportion of patients achieving an American College of Rheumatology 20 (ACR20) response.

2.2 Secondary objectives

To evaluate:

- The efficacy of secukinumab 150 mg compared to placebo at Week 16 in patients with active PsA based on the proportion of patients achieving an American College of Rheumatology 20 (ACR20) response.
- The efficacy of secukinumab 300 mg and 150 mg compared to placebo at Week 16 based on the proportion of patients with dactylitis in the subset of patients who have dactylitis at baseline.
- The efficacy of secukinumab 300 mg and 150 mg compared to placebo at Week 16 based on the proportion of patients with enthesitis in the subset of patients who have enthesitis at baseline.
- The efficacy of secukinumab 300 mg and 150 mg compared to placebo at Week 16 in subset of patients with active PsA and number of tender and swollen joints less than 10 at baseline based on the proportion of patients achieving ACR20, ACR50, and ACR70 responses
- The efficacy of secukinumab 300 mg and 150 mg compared to placebo at Week 16 based on the proportion of patients achieving ACR50 and ACR70 responses.
- The efficacy of secukinumab 300 mg and 150 mg compared to placebo at Week 16 based on the proportion of patients achieving Minimal Disease Activity (5 of the following 7 criteria: ≤ 1 tender joint, ≤ 1 swollen joint, PASI ≤ 1 or IGA mod 2011 ≤ 1 , patient assessment of pain (0-100 Visual Analog Scale (VAS)) ≤ 15 , patient global assessment of disease (VAS) ≤ 20 , HAQ-DI ≤ 0.5 , tender enthesal points ≤ 1).
- The efficacy of secukinumab 300 mg and 150 mg compared to placebo at Week 16 based on the proportion of patients achieving a PASI75, PASI90, and PASI100 responses
- The efficacy of secukinumab 300 mg and 150 mg compared to placebo at Week 16 based on the change from baseline in DAS28-CRP.
- The efficacy of secukinumab 300 mg and 150 mg compared to placebo at Week 16 based on the change from baseline in Psoriatic Arthritis Disease Activity Score (PASDAS).
- The efficacy of secukinumab 300 mg and 150 mg compared to placebo at Week 16 based on the change from baseline in SF12.
- The efficacy of secukinumab 300 mg and 150 mg compared to placebo at Week 16 based on the change from baseline in HAQ-DI.

- The overall safety and tolerability of secukinumab 300 mg and 150 mg compared with placebo as assessed by vital signs, clinical laboratory values, and adverse events (AE) monitoring.

3 Investigational plan

3.1 Study design

This study uses a multicenter, randomized, double-blind, placebo-controlled, parallel-group design. Approximately 250 adult patients (in 2:2:1 ratio; 100 secukinumab 300 mg, 100 secukinumab 150 mg and 50 placebo) with active PsA and a target skin lesion with PASI score of 1 or greater will be randomized from approximately 65 investigative sites in the United States.

Screening will be flexible in duration based on the time required to wash out prior anti-rheumatic medications and have a duration of up to 8 weeks before randomization, followed by a treatment period up to Week 52.

Patients that do not require a washout can proceed onto the baseline visit once all inclusion criteria and none of the exclusion criteria are met.

At baseline (BL), patients whose eligibility is confirmed will be randomized to one of three treatment groups and will enter the Placebo Controlled Treatment Period

Treatment Period 1

The Treatment Period 1 is defined as starting from Randomization through Week 16 (prior to the Week 16 dose). At the start of the Placebo-Controlled Treatment Period, patients will be randomized via IRT in a 2:2:1 ratio to one of three treatment groups (secukinumab 300 mg s.c., secukinumab 150 mg s.c. or placebo s.c.).

- **Group 1- Secukinumab 300 mg:** secukinumab 300 mg (two s.c. injections of the 150 mg dose) once weekly for five weeks (at Baseline, Weeks 1, 2, 3, and 4), followed by dosing every four weeks.

[figure not shown]
- **Group 2- Secukinumab 150 mg:** secukinumab 150 mg (one s.c. injection of the 150 mg dose and one s.c. secukinumab injection of placebo) once weekly for five weeks (at Baseline, Weeks 1, 2, 3, and 4), followed by dosing every four weeks.
- **Group 3- Placebo:** placebo (two s.c. injection of 150 mg secukinumab placebo per dose) once per week for five weeks (at Baseline, Weeks 1, 2, 3, and 4), followed by dosing every four weeks.

Treatment Period 2

- Patients receiving secukinumab 300 mg (**Group 1**) will continue to receive the same dose up to Week 48.
- At Weeks 16, 28 and 40 patients on secukinumab 150 mg (**Group 2**) will be classified as responders ($\geq 20\%$ improvement from BL in both tender and swollen joint counts) or non-responders.
 - At Weeks 16, 28 and 40 patients on secukinumab 150 mg (Group 2) who are responders will continue to receive secukinumab 150 mg (1.0 mL) plus placebo (1.0 mL) every 4 weeks until next evaluation of responder status at weeks 28 or 40.
 - Patients who did not meet the responder criteria at Week 16, 28 or 40 will start receiving secukinumab 300 mg s.c. every 4 weeks and will continue this dose up to Week 48.
- Patients on placebo (**Group 3**) regardless of their responder status will start receiving secukinumab 300 mg s.c. every 4 weeks from Week 16 up to Week 48.

Rescue medication will not be allowed during the day of the clinical visit and before completion of Week 16 assessments ([Section 5.5.6](#)). Although no subject will be restricted from receiving necessary rescue medications for lack of benefit or worsening of disease, patients will be discontinued from the study if rescued with prohibited biologics (as described in [Section 5.5.8](#)) and should obtain end of study assessments at the earliest possible date, provided consent to do so has not been withdrawn.

Figure 3-1 Study design

